8.10.2. Responsibilities of the Investigator

For any AE or special situation mentioned above, the Investigator must:

- **Note in the participant's medical file** the date on which the Investigator learned of the event (at a follow-up visit or a telephone contact with the participant or a third person, etc.) and any other relevant information that the Investigator has learned of the event.
- **Assess** the event in terms of seriousness, severity, and causality.
- **Report the event to the Sponsor** using the AE form.
- **Document** the event with additional useful information.
- Ensure the **follow-up** of the event.
- **Fulfil Investigator regulatory obligations** to the Competent Authorities and/or to the IRB/IEC, in accordance with local regulations.
- **Demonstrate oversight of data reported** and ensure the whole content's accuracy, completeness, and legibility in accordance with the GCP (see Section 14.1).

Moreover, the Investigator must report to the Sponsor and/or to the IRB/IEC and/or to the Competent Authorities in accordance with the local regulation, any new information that might materially influence the benefit-risk assessment of the test drug or that would be sufficient to consider changes in the test drug administration or in the overall conduct of the clinical investigation.

8.10.2.1. Documentation of the Event

The Investigator must ensure that all events are well documented and provide the Sponsor, on request, with anonymized copies of relevant documents (e.g., autopsy report and terminal medical reports [[ICH E6 \(R2\)](#)]).

8.10.2.2. Follow-up of Adverse Events

The Investigator must ensure that follow-up of the participant is appropriate to the nature of the event, and that it continues until resolution if deemed necessary.

Any change in terms of diagnosis, severity (improvement), seriousness, measures taken, causality, or outcome regarding an AE already reported must be written up in a new complete evaluation of the event documented on the Adverse Event form previously created for the event.

In case of worsening of severity, a new complete evaluation of the event must be documented on a new Adverse Event form. If the AE has not resolved at the participant's final visit in the study, the participant must be followed up suitably and any information on the outcome of the event noted on the Adverse Event form previously created for the event.

If the follow-up of the participant is not done by the Investigator (e.g., hospitalization, followed by a specialist or the participant's general practitioner), the Investigator will do everything possible to establish/maintain contact with the person/department in charge of follow-up of the participant.

8.10.2.3. Special Situations (Pregnancy, Overdoses, Intake of IMP by a Person Around the Participant)

Pregnancy

If a female participant in the study becomes pregnant, the Investigator must:

- Stop immediately the test drug (if the pregnancy is a non-inclusion/exclusion criterion).
- Report it on the specific eCRF Pregnancy form and notify the Sponsor immediately (*i.e.*, without delay and within 24 hours of awareness at the latest).
- Pregnancy should not be reported as an AE except in the following circumstances:
 - If it is associated with an AE. This consequence itself should be reported as an AE.
 - While pregnancy itself is not considered to be an AE, any pregnancy complication or elective termination of a pregnancy for medical reasons will be reported as an AE. Abnormal pregnancy outcomes (*e.g.*, spontaneous abortion, fetal death, stillbirth, congenital anomalies, ectopic pregnancy) are considered SAEs and will be reported as such.
- Contribute to the follow-up of this pregnancy and provide the Sponsor with information concerning this follow-up (notably using the second page of the specific paper Pregnancy form).

If the partner of a participant becomes pregnant during the study, the pregnancy should not be reported in the eCRF. The Investigator should **immediately** contact the Sponsor (contact details provided in the Investigator's study file) who will determine the procedure to be followed.

Overdose of IMP

- In case of overdose, the Investigator should report it on the IMP administration page. Overdose should not be reported as an AE except in the following circumstances:
 - The overdose is associated with an AE. This consequence itself should be reported as an AE.
 - The overdose is intentional with possible suicidal/self-harming intent should be reported as an AE regardless of sequelae.
- Overdose should be followed up to ensure that the information is as complete as possible with regard to:
 - Dose details (number of units, duration, etc.) and, if multiple overdoses, details regarding other medicinal products or substance, context of occurrence (*i.e.*, intentional [suicide attempt, other reason] or accidental [error in prescription, administration, dispensing, dosage]), related signs and symptoms ("No related adverse events" to be reported otherwise), and outcome.
- Insofar as possible, a blood sample should be collected for assay of the IMP taken.

Intake of IMP or Occupational Exposure by a Person Around the Participant

This event should not be reported in the eCRF. The Investigator should **immediately** (*i.e.*, without delay and within 24 hours of awareness at the latest) contact the Sponsor (contact details provided in the Investigator's study file) who will determine the procedure to be followed.

8.10.2.4. Recording Methods in the eCRF

Adverse events must be documented on the Adverse Event form of the eCRF.

In case of chronic disease:

- If the disease is known when the participant enters in the study, only worsening (increased frequency and/or intensity of the episodes/attacks), this will be documented as an AE.
- If a disease is detected during the study and if repeated episodes enable diagnosis of a chronic disease, the episodes will be grouped on the Adverse Event form previously created for the event, which will clearly describe the diagnosis.

8.10.2.5. Procedure for an Event Requiring an Immediate Notification

In case of an event requiring an immediate notification, the Investigator must:

- **Immediately** after being informed of this event, **fill in the participant's medical file** as well as the **Adverse Event form** of the eCRF (for SAEs and AESIs if applicable) according to the general instructions available in the eCRF, without waiting for the results of the clinical outcome or of additional investigations. When data will be submitted into the eCRF an email will be immediately and automatically sent to the Sponsor. However, for special situations requiring an immediate notification (as defined in Section 8.10.2.3) the completion of the Adverse Event form should not be performed systematically.
- If requested by the Sponsor (person designated in the contact details provided in the Investigator's study file), provide anonymized copies of the documents that provide additional useful information.
- Fulfil Investigator regulatory obligations to the Competent Authorities and/or to the IRB/IEC, in accordance with local regulations.
- In case of an SAE occurring in a first-in-human study, if the Investigator establishes or even suspects a relationship with the study protocol, they must immediately suspend the administration of IMP (and AxMP if applicable) in all participants. In this case, the written consent of the enrolled participants must be obtained again before the study is resumed.

Moreover, on request, the Investigator should provide the Sponsor with the documents required in Section 8.10.2.1.

If an AE that is initially non-serious worsens and becomes an SAE, this must be reported **immediately** on an “Adverse Event” form of the eCRF.

In case the eCRF is unavailable when the Investigator was informed of an AE to be reported immediately, the Investigator should:

- **Immediately** fill in a paper Adverse Event page:
 - For serious event, on a paper Adverse Event – Initial Information page.
 - For event initially non-serious, on a paper Adverse Event – Initial Information page, and the worsening leading to seriousness on a paper Adverse Event – Additional Information page.
- Immediately send the page(s) by email to the person(s) designated in the contact details provided in the Investigator's study file or outside working hours, the 24-hour phone number.
- As soon as the eCRF becomes available, the Investigator should enter these data in the Adverse Event form of the eCRF.

8.10.3. Responsibilities of the Sponsor

In accordance with international guidance, the assessment of the seriousness and the causality of AEs is usually made by the Investigator but falls also under Sponsor's duties, who is responsible for ensuring that all suspected unexpected serious adverse reactions are reported to Competent Authorities and Ethics Committees.

The Sponsor will review the seriousness of the AEs and the causality of (at least) the SAEs, whether reported by the Investigator or upgraded by the Sponsor. The causality and the seriousness may be upgraded (but never downgraded). Anonymized copies of documents providing useful information such as reports of further consultations, laboratory test reports, and reports of other examinations aiding diagnosis may be requested for the event assessment. If the assessments of the Investigator and the Sponsor are different, both will be reported in the clinical study report (CSR).

In addition, the Sponsor is responsible for determining whether an AE is **expected or unexpected**. An AE will be considered unexpected if the nature, severity, or frequency of the event is not consistent with the risk information previously described for the IMP.

Independently of the regulatory obligations of the Investigator, the Sponsor must report the pharmacovigilance data and any new safety finding likely to affect the benefit/risk balance of the product, required in ICH GCP guidelines and local regulations, to the appropriate Authorities, to all the Investigators involved, and to the trial participants involved (through the Investigators) as described in Section 13.4. **Responsibilities of Data Review Committee**

During the Safety Lead-in phase, the DRT, composed of Investigator(s) and the Sponsor's medical, safety, and statistical representative(s), will meet to evaluate clinical and laboratory safety data in order to make decisions regarding determination of the RCD. The DRT will meet at minimum:

- Before deciding that a dose is the RCD and the Expansion phase can be opened.
- If the rate of DLTs indicates that the dose should be de-escalated, the DRT will meet to determine if the 250 mg QD dose should be tested.
- If either the 500 mg and/or the 250 mg dose is determined to have unacceptable toxicity.

8.12. Dose Modification and Management for Adverse Events

8.12.1. Study Treatment Dose Modification and Management Associated with Ivosidenib

For any AE, including AEs not specifically mentioned in [Table \(8.12.1\) 1](#), the Investigator may decide to delay dosing or modify the dose of ivosidenib based on clinical judgment. These decisions should be discussed with the Sponsor prior to implementation. Dose modifications of ivosidenib from 500 mg to 250 mg will be permitted on study for management of AEs ([Table \(8.12.1\) 1](#)). If more than one AE occurs that would require a dose modification, upon resolution of all AEs to baseline or Grade 1, ivosidenib should be dose reduced to 250 mg. Re-escalation may be allowed with approval from the Sponsor.

Dose delays are discouraged, except as needed for management of AEs. Dose delays up to 28 days will be permitted at the discretion of the Investigator in consultation with the Sponsor for reasons including management of AEs and for mitigating circumstances (e.g., planned procedures). Palliative biliary decompression procedures will be permitted on study and will not require interruption of ivosidenib (see Section 8.12.5).

If the subject cannot resume ivosidenib within 28 days, the subject should be discontinued from ivosidenib. Other reasons for treatment termination are provided in Section 5.4.1. If ivosidenib is discontinued, the subject may continue receiving nivolumab and ipilimumab or nivolumab alone. If subject permanently discontinues treatment from all three drugs, the EOT and Safety Follow-up visits will be completed as well as the PFS follow-up (if disease has not progressed) and Survival Follow-up visits. Exemptions may be considered for those subjects who are determined by the Investigator to have received clinical benefit from treatment. If a dose is delayed for the management of an AE, the subject should resume the study at the next planned visit within a dosing cycle.

If a strong CYP3A4 inhibitor must be co-administered, reduce the ivosidenib dose to 250 mg QD. If the strong inhibitor is discontinued, increase the ivosidenib dose (after at least 5 half-lives of the strong CYP3A4 inhibitor) to the recommended dose of 500 mg QD.

Table (8.12.1) 1 - Management of Ivosidenib related QT Prolongation and Adverse Events by NCI CTCAE Grade

NCI CTCAE Grade	Management
Grade 2: Average QTc interval greater than 480 msec up to 500 msec	
 Monitor and supplement electrolyte levels as clinically indicated. Review and adjust concomitant medications with known QTc interval-prolonging effects. Interrupt ivosidenib. Restart ivosidenib at 500 mg once daily after the QTc interval returns to less than or equal to 480 msec. Monitor ECGs should be conducted at least weekly for 2 weeks following resolution of QTc prolongation.
Grade 2 nausea or vomiting (related or unrelated)	
 Consider holding dose of ivosidenib until resolution of adverse event (AE) to Grade ≤ 1 within 28 days of supportive therapy. Manage with supportive therapy according to the institutional standard of care. May resume ivosidenib at same dose.
Grade 3: Average QTc interval greater than 500 msec	
 Monitor and supplement electrolyte levels as clinically indicated. Review and adjust concomitant medications with known QTc interval-prolonging effects. Interrupt ivosidenib. Resume ivosidenib at a reduced dose of 250 mg once daily when QTc interval returns to within 30 msec of baseline or less than or equal to 480 msec. Monitor ECGs at least weekly for 2 weeks following resolution of QTc prolongation. Consider re-escalating the dose of ivosidenib to 500 mg daily if an alternative etiology for QTc prolongation can be identified.

NCI CTCAE Grade	Management
Grade 3 AEs (related, first event)	
 Interrupt ivosidenib until toxicity resolves to Grade 1 or lower, or baseline, then resume at 250 mg, or re-escalation to 500 mg with Sponsor approval. If Grade 3 toxicity recurs (a second time), interrupt ivosidenib dose until the toxicity resolves, then resume 250 mg daily. If Grade 3 toxicity recurs (a third time), discontinue ivosidenib.
Grade 4 AEs (related) including QTc interval prolongation with signs/symptoms of life-threatening arrhythmia	
 Discontinue ivosidenib permanently.

Abbreviations ECG = electrocardiogram; NCI CTCAE = National Cancer Institute Common Terminology Criteria for Adverse Events; QTc = heart rate-corrected QT interval; QTcF = heart rate-corrected QT interval using Fridericia's method.

Note Per NCI CTCAE, version 4.03.

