6.3.2.2. Concomitant Therapies Requiring Careful Monitoring (Use with Caution)

Based on the results of in vitro and in vivo studies, the following therapies should be avoided and replaced with alternative treatments. If this is not possible, participants receiving these drugs should be carefully monitored.

- Concomitant use of drugs with a potential for QT prolongation should be avoided and replaced with alternative treatments. If this is not possible, subjects receiving these drugs

should be adequately monitored by ECG controls, drug concentration (where applicable), and serum electrolytes (*i.e.*, potassium and magnesium).

These medications include but are not limited to:

- Fluoroquinolones such as, ciprofloxacin and moxifloxacin.
- Azole antifungals such as fluconazole and posaconazole.
- Serotonin (5-HT3) antagonists such as granisetron and ondansetron. See [Appendix 10](#), Table 4 for a complete list of medications known to prolong the QT interval.

- Moderate or strong inhibitors of CYP3A4: Ivosidenib clinical trials and physiologically based pharmacokinetic simulations have shown that ivosidenib plasma concentrations increase with co-administration of a strong or moderate CYP3A4 inhibitor, and increased ivosidenib plasma concentrations may increase the risk of QTc prolongation. Therefore, alternative therapies that are not moderate or strong CYP3A4 inhibitors should be considered during treatment with ivosidenib. If concomitant use of moderate CYP3A4 inhibitors is unavoidable, subjects should be monitored for increased risk of QTc prolongation. If a strong CYP3A4 inhibitor must be co-administered, reduce the ivosidenib dose to 250 mg QD. If the strong inhibitor is discontinued, increase the ivosidenib dose (after at least 5 half-lives of the strong CYP3A4 inhibitor) to the recommended dose of 500 mg QD (see Table 5 in [Appendix 10](#)).
- Sensitive substrates of CYP2C9: Ivosidenib may also induce CYP2B6, CYP2C8, and CYP2C9. Consider alternative therapies that are not sensitive substrates of CYP2C9 (*e.g.*, phenytoin, warfarin). Monitor INR levels more frequently in subjects receiving warfarin (a CYP2C9 substrate) during initiation or discontinuation of ivosidenib.
- Coadministration of ivosidenib may decrease the concentrations of hormonal contraceptives. Consider alternative methods of contraception in subjects receiving ivosidenib as described [Appendix 7](#).

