8.6.1.1. Management of QT Prolongation

Events of QT prolongation (*i.e.*, QTcF Grade ≥ 3) should be reported as AESIs to the Sponsor within 24 hours, according to expedited reporting procedures (see Section 8.3).

Subjects may be at increased risk for the development of QT prolongation when treated with ivosidenib in combination with fluoroquinolones, azole antifungal agents, or serotonin (5-HT3) antagonists. Investigators must be vigilant; refrain from administering concomitant medications associated with QT prolongation and if no other therapeutic options are available, monitor subjects receiving study treatment with the combination of these drugs and evaluate ECG and electrolytes (including potassium, magnesium, and calcium), particularly in subjects presenting with nausea, vomiting, or diarrhea. Systemic administration of a moderate or strong CYP3A4 inhibitor requires careful monitoring of QTcF.

Subjects who experience QT prolongation (*i.e.*, QTcF > 480 msec; NCI CTCAE Grade ≥ 2) while receiving study treatment should be promptly evaluated for causality of the QT prolongation and managed according to the following guidelines.

- Levels of electrolytes (potassium, calcium, and magnesium) should be checked, and supplementation given to correct any values outside the normal range.
- Concomitant therapies should be reviewed and adjusted as appropriate for medications with known QT prolonging effects.
- If no other cause is identified and the Investigator believes it is appropriate, particularly if QTcF remains elevated (after the above measures have been implemented, or as determined by the Investigator), study treatment may be interrupted, and an ECG should be rechecked in approximately 1 week after the QT prolongation event was first observed or more frequently as clinically indicated.

Please refer to [Table \(8.12.1\) 1](#) for the management of QT prolongation by NCI CTACE grade.

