8.12.3. Dose Modification for Ivosidenib, Nivolumab and Ipilimumab

When study interventions are administered in combination, attribution of an AE to a single component is likely to be difficult. When an AE cannot be clearly attributed to any one or combination of drugs, the most stringent criteria for dose modification (based on Dose modification for ivosidenib and ipilimumab/nivolumab - [Table \(8.12.1\) 1](#) and [Appendix 8](#)) must be used for all three drugs.

Dose delay: When study interventions are administered in combination, if the AE is considered immune-related, both nivolumab and ipilimumab interventions should be held according to recommended dose modifications ([Appendix 8](#)). QTc prolongation and other Grade3 or higher adverse events that are possibly related to ivosidenib should be managed according to dose modification recommendations in [Table \(8.12.1\) 1](#).

Re-starting Study Interventions: Subjects may not have any dose modifications (no change in dose or schedule) of nivolumab and/or ipilimumab in this study. At the 250 mg QD dose level, no dose re-escalation is allowed for ivosidenib. If the toxicity does not resolve or the criteria for resuming treatment are not met, the subject must be discontinued from all study interventions. If the toxicities do resolve and conditions are aligned with what is defined in [Appendix 8](#) and [Table \(8.12.1\) 1](#) ivosidenib, nivolumab and/or ipilimumab may be restarted at the discretion of the Investigator.

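### The Grade 2 QTc row restarts ivosidenib at 500 mg without regard to the prior dose, so as written it doubles the dose of a participant on 250 mg after a QTc event

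*Protocol*

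**What the plan says.** In Protocol Table (8.12.1) 1, the row for Grade 2 QTc prolongation (above 480 and up to 500 msec) tells the site to check electrolytes, review QT-prolonging medication and interrupt ivosidenib. It then says: "Restart ivosidenib at 500 mg once daily after the QTc interval returns to less than or equal to 480 msec". At least weekly ECGs follow for 2 weeks.

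Two sections route QTc events to this table. Section 8.6.1.1 refers to it "for the management of QT prolongation by NCI CTACE grade". Section 8.12.3 names the same table at the end of a sentence that begins "QTc prolongation and other Grade3 or higher adverse events that are possibly related to ivosidenib should be managed according to dose modification recommendations in". Neither mentions the participant's current dose.

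Other dose rules bear on the same participant:
- Section 8.12.3: "At the 250 mg QD dose level, no dose re-escalation is allowed for ivosidenib".
- Section 8.12.1: "If a strong CYP3A4 inhibitor must be co-administered, reduce the ivosidenib dose to 250 mg QD". Sections 6.3.2.2 and 8.12.1 allow an increase only after the inhibitor has been stopped for at least 5 of its half-lives.
- Grade 3 QTc row of the same table: resume at 250 mg, and consider 500 mg only if another cause of the prolongation is identified.
- Section 8.12.1, on reductions for adverse events: "Re-escalation may be allowed with approval from the Sponsor".

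The text before the table describes its scope: "Dose modifications of ivosidenib from 500 mg to 250 mg will be permitted on study for management of AEs".

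**The concern.** A restart rule should return a participant to the dose already in use or to a lower one. This row names a fixed dose. The protocol can put a participant on 250 mg through assignment to the 250 mg level, de-escalation of a whole cohort, reduction after a DLT or a Grade 3 event, or a strong CYP3A4 inhibitor. For any of them, following the row means going up in dose because of a QTc event.

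The stake is patient safety. Section 2.5 lists QT prolongation as an important identified risk of ivosidenib in all subjects, and Section 4.1.3.1 says the risk rises with peak plasma concentration. The inhibitor route is the most exposed, because 500 mg with a strong inhibitor gives higher concentrations than 500 mg alone, and Section 6.3.2.2 warns that "increased ivosidenib plasma concentrations may increase the risk of QTc prolongation".

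**Working it through.** The plan has no figure to reproduce here. The check is one ratio and a comparison of rules.

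**Dose factor.** Factor = restart dose in the row / dose before interruption.
- Participant on 500 mg: 500/500 = 1.
- Participant on 250 mg: 500/250 = 2.

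**Exposure factor.** Section 4.1.3.1 says exposure rises less than dose-proportionally from 200 to 1,200 mg once daily. Doubling the dose from 250 mg therefore gives an exposure factor above 1 and below 2. The documents do not give the value.

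**Rules side by side, for a participant on 250 mg.**

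| How the participant came to 250 mg | Source | What otherwise governs a return to 500 mg | Grade 2 QTc row |
|---|---|---|---|
| Assigned to the 250 mg level | Protocol 4.1.4.1 | Barred by 8.12.3 | 500 mg |
| Whole cohort de-escalated (DLT rate 33% or more) | 4.1.4.5 | Barred by 8.12.3, if the bar covers anyone on 250 mg | 500 mg |
| Resumed after a DLT | 4.1.4.3 | Resumption is at 250 mg; 8.12.1 Sponsor approval, if read generally | 500 mg |
| Reduced after Grade 3 QTc | Table (8.12.1) 1 | Considered only if another cause is found | 500 mg |
| Reduced after another related Grade 3 event | Table (8.12.1) 1 | Sponsor approval, stated in that row | 500 mg |
| Strong CYP3A4 inhibitor | 6.3.2.2, 8.12.1 | Not while it is given; then a wait of at least 5 half-lives | 500 mg |

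The last column never changes, and none of the conditions in the third column appears in the Grade 2 QTc row.

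**Ordering within the table.** Take a participant already on 250 mg. After a Grade 3 QTc event the table resumes 250 mg: 250/250 = 1. After a milder Grade 2 event it restarts 500 mg: 500/250 = 2. The less severe event leads to the higher dose.

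**Wording elsewhere in the table.** The Grade 2 nausea or vomiting row lets the participant resume the same dose. The form of words that avoids the problem is therefore already in use.

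**After the proposed change.** 500/500 = 1 and 250/250 = 1, with no increase on any route.

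**The case against.** The strongest reply is that the table assumes a participant on 500 mg. Its lead-in speaks only of going from 500 mg to 250 mg, and calling 250 mg a reduced dose in the Grade 3 QTc row makes sense only from 500 mg. That is probably what the drafters had in mind. But the assumption is not stated, and the two sections that send QTc events to the table do not make it.

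Second, a sensible reader would apply the rules together. The bar in Section 8.12.3 sits in the same paragraph as a pointer to the table, and the inhibitor rule stands just before the table as a continuing condition. This is a fair way to reconcile the text, but nothing says that these rules override the row. The most-stringent-criteria rule in Section 8.12.3 does not settle it either: it concerns events that cannot be clearly attributed to a drug, and it compares the table with Appendix 8.

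Third, there are safeguards. Section 8.6.1.1 has electrolytes corrected and medication reviewed, leaves interruption to the Investigator's judgment, and asks for careful QTcF monitoring with strong inhibitors. Section 8.12.1 wants Investigator dose changes discussed with the Sponsor first. Restart also requires QTc of 480 msec or less. All of this lowers the chance of harm without saying which dose is correct. Medication review targets drugs with known QT effects, which is not the same property as CYP3A4 inhibition.

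Four stronger readings are tempting and are not supported:
- That the row orders 500 mg for everyone. It does not say so; the breadth comes from a missing qualifier.
- That the increase is automatic. Sections 8.6.1.1 and 8.12.1 put judgment and Sponsor discussion in the way.
- That Section 8.12.1 makes Sponsor approval a general condition of every re-escalation. The sentence follows one about several adverse events occurring together and may be confined to that case.
- That 500 mg is itself an unsafe dose. Section 4.1.3.1 gives it as the approved dose for this disease and places the QT concern above 500 mg.

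**Conclusion.** The row is wrong as written, not merely short of detail. For a participant on 250 mg it states a dose twice the one being taken, straight after a QTc event. It contradicts the re-escalation bar, the strong-inhibitor rule and the Grade 3 QTc row, and it may also bypass Sponsor approval.

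The conclusion rests on reading the row literally, since no text restricts it. It does not depend on how wide the bar in Section 8.12.3 is: whether the bar covers only those assigned to 250 mg or anyone on that dose, the row conflicts with it for at least the first group.

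The practical reach is small. SAP Section 5 records that enrollment stopped after 7 patients, and no document shows that any of them took 250 mg. No estimate or analysis is affected, and the documents do not support any inference that a participant was harmed. The row could still matter for anyone remaining on ivosidenib: Protocol Section 4.3.1 lets participants who are benefiting continue if the study ended for reasons other than safety, and the documents do not give the reason.

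**What to change.** Replace the restart sentence in the Grade 2 QTc row with:

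> Once QTc is 480 msec or less, restart ivosidenib at the dose the participant was taking immediately before the interruption (500 mg or 250 mg once daily). The strong CYP3A4 inhibitor rule and the limits on re-escalation in Sections 8.12.1 and 8.12.3 continue to apply.

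The second sentence is needed for a participant on 500 mg who starts a strong inhibitor during the interruption; without it the prior dose would be too high.

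The cost is the wording of one table row. Visits, sample size and analyses do not change. Management of participants on 500 mg also stays the same, apart from making explicit that the inhibitor rule still holds. All that is given up is a literal instruction to move participants from 250 mg to 500 mg after Grade 2 QTc prolongation.
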